6 DATA COLLECTION AND ANALYSIS

6.1 DATA COLLECTION

For each subject who meets inclusion criteria, a clinical report form (CRF) must be completed and signed by the investigator to certify that the data within each CRF are complete and correct according to data collection schedule (Appendix I). Every effort

should be made to respond to all questions on each CRF page, completion of the data is required by the protocol. The header section of each CRF page should be completed to identify the Investigators/surgeon and subject identification.

Upon receipt of completed CRFs and prior to entering data into the aggregate data summary table, the site-coordinator will ensure the accuracy of data recorded by comparison to supporting source documents. Adherence to proper recording of information as well as assuring that corrections are being made will also be addressed.

One interim analysis will be conducted when the first half of patients in each group (35 treatment and 35 control) complete their 30-day follow-up visit. Specifically, the interim analysis will be blinded and conducted at a nominal 0.0031 one-sided level of significance, while the final analysis will be conducted at a nominal 0.0219 one-sided level of significance. These values were calculated using a third-degree Kim-DeMets power alpha-spending function evaluated at the halfway point. If the actual information fraction at the time of the analysis is different, or the DSMC requests additional unblinded analysis, the significance levels will be adjusted using the alpha-spending function.

Results of the interim analysis will determine if it is futile to continue patient enrollment based on statistically significant differences (24 hour decrease in the time to return of bowel function in the treatment group compared to controls at a one-sided 2.5% significance level between the treatment and control groups). In addition, the MCW IRB in collaboration with the study investigators may terminate the study at any time to maintain patient safety.

The following table shows the probability of early stopping and the overall power of the study for various hypothetical effect sizes. If the design assumptions are correct, the study will stop early for efficacy with 23% probability, but if the actual effect is 50% larger (due to larger mean difference or smaller within-group standard deviation), then the trial will stop early 60% of the time.

Relative effect size*	Probability of concluding superiority of the intervention		
	At interim analysis	At final analysis	Overall
0	0.31%	2.19%	2.5%
0.5	4.1%	24.6%	28.7%
1	22.9%	57.1%	80.0%
1.5	60.0%	38.8%	98.8%
2	89.4%	10.1%	99.9%

* The relative effect size is the ratio of the actual effect size to the design effect size of 24 hour difference with 48-hour within-group standard deviation.

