4.3.3 SAMPLE SIZE DETERMINATION

A total of 140 patients are expected to undergo research related treatments. The study will contain one open surgery arm. The open surgery arm will be a single-site prospective, randomized, double-blinded, placebo-controlled clinical trial with 1:1

randomization between the study drug and placebo with 70 patients in each group for a total of 140 patients in the study. An interim evaluation of efficacy will be conducted separately in the open surgery arm when half the patients have been recruited.

This study is expected to enroll up to 140 subjects from one academic medical center (Froedtert Hospital and the Medical College of Wisconsin) a site that performs state of the art hernia repairs and is a high volume hernia practices.

The study has been designed to provide at least 80% power to detect a 24-hour decrease in the time to return of bowel function in the treatment group compared to the control group at a one-sided 2.5% significance level. This corresponds to a two-sided 5% significance level, but acknowledges the one-sided nature of the study hypothesis. Based on data from studies of the experimental treatment in other contexts, as well as internal data, we expect a standard deviation of 48 hours. Adjusting for the increase in sample size to accommodate the planned interim analysis, 64 evaluable patients per group will provide the desired power. More details of the power characteristics are shown under the Interim Analysis section. We will recruit 70 patients in each arm to accommodate a 5-10% dropout rate.

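### The final-look level of 0.0219 is the alpha left over after the interim, not the nominal level the spending function gives (0.0237), and it contradicts the plan's own power table

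*Combined protocol and SAP*

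**What the plan says.** Section 4.3.3 sets the overall error rate "at a one-sided 2.5% significance level. This corresponds to a two-sided 5% significance level". It aims for at least 80% power for a 24-hour difference, where "we expect a standard deviation of 48 hours". After allowing for the interim look, it concludes that "64 evaluable patients per group will provide the desired power".

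Section 6.1 puts one interim analysis at the halfway point, at a nominal one-sided level of 0.0031, and adds that "the final analysis will be conducted at a nominal 0.0219 one-sided level of significance". On where the two levels come from, it says: "These values were calculated using a third-degree Kim-DeMets power alpha-spending function evaluated at the halfway point". The levels are to be recomputed from the spending function if the actual information fraction differs or the DSMC asks for additional unblinded analysis.

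The table that follows is headed "Probability of concluding superiority of the intervention". It splits that probability into interim, final and overall for five relative effect sizes. With no effect it prints 0.31%, 2.19% and 2.5%. At the design effect it prints 22.9%, 57.1% and 80.0%. At twice the design effect it prints 89.4%, 10.1% and 99.9%.

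**The concern.** The same figure, 0.0219, serves two purposes. In the text it is the p-value threshold for the final test. In the no-effect row of the table it is the probability of first crossing the boundary at the final look. These are different quantities. At the first look, alpha spent and nominal level coincide. At the second they do not, because some trials that would reject at the end have already stopped at the interim. The nominal level must therefore exceed the increment.

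What is at stake is the decision rule. A final one-sided p-value between 0.0219 and 0.0237 fails under the text but succeeds under the design that produced the table. That has to be settled before unblinding, since a later change would look driven by the data.

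**Working it through.** **Inputs.** One-sided alpha 0.025, difference 24 h, SD 48 h and 64 evaluable per group (section 4.3.3). Spending function α(t) = 0.025·t³ at t = 0.5, nominal levels 0.0031 and 0.0219, and the power table (section 6.1). Student's t-test (section 6.3).

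**Step 1: interim level.** α(0.5) = 0.025 × 0.125 = 0.003125, so z₁ = 2.734. This reproduces the plan's 0.0031.

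**Step 2: where 0.0219 comes from.** 0.025 − 0.003125 = 0.021875, which rounds to 0.0219. It is the incremental alpha.

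**Step 3: the nominal final level.** Under no effect, Z₁ and Z₂ are bivariate normal with correlation √0.5 = 0.707. Solve P(Z₁ < 2.734, Z₂ ≥ c) = 0.021875. The result is c = 1.9825, nominal level 0.0237. Starting from the rounded interim level of 0.0031 also gives 0.0237. The stated 0.0219 corresponds to c = 2.016.

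**Step 4: reproduce the plan's table.** The drift that gives exactly 80.0% power with the 0.0237 boundary is 2.816. From drift = 24 / (48·√(2/n)), n = 2 × (2.816 × 48/24)² ≈ 63.4 per group. At that drift (interim / final / overall, %):

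| Relative effect | Plan's table | Final level 0.0237 | Final level 0.0219 |
|---|---|---|---|
| 0 | 0.31 / 2.19 / 2.5 | 0.31 / 2.19 / 2.50 | 0.31 / 2.01 / 2.32 |
| 0.5 | 4.1 / 24.6 / 28.7 | 4.1 / 24.6 / 28.7 | 4.1 / 23.5 / 27.6 |
| 1 | 22.9 / 57.1 / 80.0 | 22.9 / 57.1 / 80.0 | 22.9 / 56.2 / 79.1 |
| 1.5 | 60.0 / 38.8 / 98.8 | 60.0 / 38.8 / 98.8 | 60.0 / 38.7 / 98.7 |
| 2 | 89.4 / 10.1 / 99.9 | 89.4 / 10.6 / 99.99 | 89.4 / 10.6 / 99.99 |

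The first four rows match 0.0237 to the printed precision. With 0.0219 the final and overall cells of those rows do not match.

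**Step 5: last row.** 89.4 + 10.1 = 99.5, not 99.9. Both boundaries give 10.6 in the final cell, so this is a separate misprint and says nothing about which threshold was used.

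**Step 6: power at 64 per group.** Drift = 24 / (48·√(2/64)) = 2.828. Power is 79.4% with 0.0219 and 80.35% with 0.0237. With 0.0219, 80% power needs 64.9, so 65 per group.

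**Step 7: the t-test itself.** Two independent simulations with looks at 32 and 64 per group gave:

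| Final level | Type I error | Power |
|---|---|---|
| 0.0219 | 2.30% and 2.36% | 78.8% and 78.6% |
| 0.0237 | 2.49% and 2.53% | 79.7% and 79.6% |

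**Step 8: another information fraction.** If 35 of 64 per group are analysed at the interim, t = 35/64 = 0.547 and the spend is 0.025 × 0.547³ = 0.0041. The increment is 0.0209, and the nominal final level is 0.0234.

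**The case against.** The arithmetic is not in dispute. The case on the other side is that it matters little.

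- **The error is conservative.** Overall alpha is 2.32%, so type I error is controlled and about 0.18 points go unspent. This stands. A stricter final level is valid if chosen knowingly, but the plan claims 2.5% and says the figure came from the spending function.
- **The power loss is under one point and depends on the evaluable number.** Recruiting 70 per group with 5–10% dropout leaves 63 to 66.5. With 0.0219, power is 78.8% at 63, 79.4% at 64, 80.1% at 65 and 82.9% if all 70 are analysed. This stands too: the shortfall below 80% applies only at the lower end of that range.
- **The correction does not secure 80% with the planned t-test.** Simulated power at 64 per group is 79.6–79.7% even with 0.0237. This is true. That residual shortfall comes from the normal approximation used for the sample size, not from the mislabelled level.
- **The adjustment clause may replace 0.0219 anyway.** It would if 35 of 64 were analysed at the interim. At exactly half information, which the text assumes, it is not triggered. If it were triggered, repeating the same subtraction would give 0.0209 instead of 0.0234.
- **The window is narrow.** A final p-value falls between the two levels with probability of about 0.9% under the design effect (57.1 − 56.2) and 0.2% under no effect (2.19 − 2.01).

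**Conclusion.** The concern holds. The nominal final level implied by the stated spending function at half information is 0.0237, and 0.0219 is the incremental alpha under the wrong label. The text and the power table therefore describe different tests. The stated test has an overall one-sided error of 2.32% against 2.5%, and power about 0.9 points lower: 79.1% against 80.0% at the table's design point, and 79.4% against 80.35% at 64 per group. There is no inflation of type I error.

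These figures assume an interim at exactly half the information, the 24-hour difference and 48-hour SD of section 4.3.3, and the normal approximation. The t-test simulations show the same gap at slightly lower power. The practical effect is small, but a prespecified decision threshold that contradicts the plan's own table should be corrected.

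**What to change.** In section 6.1, state the nominal one-sided final level as 0.0237 (critical z 1.983) at information fraction 0.5, and label 0.0219 as the incremental alpha spent at the final look. Say that both levels will be recomputed from the joint distribution of the two statistics if the fraction differs, for example about 0.0234 at 35 of 64 per group. Correct the last table row to 89.4% / 10.6% / >99.9%.

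If 0.0219 is kept on purpose, restate overall one-sided alpha as 2.3% and power as about 79% at 64 per group, and recompute the table to match.

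The first option costs one number, a label and one table row. It recovers about one percentage point of power with alpha still at 2.5%, and needs no change to sample size or conduct. It should be made before any unblinded look at the data.

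### Section 6.1 tests the interim at one-sided 0.0031 but words the stop decision as 'futile' at a 24-hour difference and one-sided 2.5%; the sentence should be reworded

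*Combined protocol and SAP*

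**What the plan says.** Section 6.1 plans one interim analysis when 35 patients per group have finished 30-day follow-up. The test is "conducted at a nominal 0.0031 one-sided level of significance", with 0.0219 at the final analysis. Both levels come from a third-degree power spending function at the halfway point. If the information fraction differs, or the DSMC asks for a further unblinded analysis, "the significance levels will be adjusted using the alpha-spending function".

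The following paragraph states what the interim results decide: "Results of the interim analysis will determine if it is futile to continue patient enrollment based on statistically significant differences". A parenthesis then defines the difference as a 24-hour decrease "in the treatment group compared to controls at a one-sided 2.5% significance level between the treatment and control groups".

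Elsewhere the look is for efficacy:

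- Section 4.3.3: "An interim evaluation of efficacy will be conducted separately in the open surgery arm".
- Section 6.1, before the table: under the design assumptions "the study will stop early for efficacy with 23% probability".
- Section 6.1, table heading: "Probability of concluding superiority of the intervention".
- Section 8 (Timeline): enrolment may end earlier if 35 per arm is enough to show a significant difference. No level is named.

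The overall design target in Section 4.3.3 is 80% power for a 24-hour decrease "in the treatment group compared to the control group at a one-sided 2.5% significance level", which is almost the wording of the 6.1 parenthesis.

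**The concern.** One look cannot be decided at both 0.0031 and 0.025. The paragraph on spending gives a test level but does not attach an action to it. The paragraph that does attach an action gives a different level and adds a 24-hour condition that neither the spending function nor the table contains. An interim p-value between 0.0031 and 0.025 could therefore be defended as a stop or as a continue from the text, after the data have been seen.

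The word 'futile' adds to the problem. Futility normally means stopping because benefit is unlikely to be shown, whereas this sentence refers to stopping because benefit has been shown. A reader may look for a futility boundary, and there is none.

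At stake is the 2.5% one-sided error rate for which the trial was designed.

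**Working it through.** **Inputs.** From Section 4.3.3: overall one-sided alpha 0.025, difference 24 h, SD 48 h, 64 evaluable per arm. From Section 6.1: interim at 35 per arm, interim level 0.0031, final level 0.0219, cubic spending at information fraction 0.5.

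**1. The plan's interim level.** 0.025 × 0.5³ = 0.003125, which rounds to the stated 0.0031.

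**2. Which level the power table uses.** Half of 64 evaluable is 32 per arm at the interim. The standard error is 48 × √(2/32) = 12.0 h, so the design effect gives an expected z of 24/12 = 2.0. The interim rejection probability is 1 − Φ(z_crit − 2.0 × relative effect), with z_crit = 2.737 for 0.0031 and 1.960 for 0.025.

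| Relative effect | Table in 6.1 | At 0.0031 | At 0.025 |
|---|---|---|---|
| 0 | 0.31% | 0.31% | 2.5% |
| 0.5 | 4.1% | 4.1% | 16.9% |
| 1 | 22.9% | 23.1% | 51.6% |
| 1.5 | 60.0% | 60.4% | 85.1% |
| 2 | 89.4% | 89.7% | 97.9% |

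The table was built on 0.0031.

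**3. Where the two statements disagree.** At 35 per arm and SD 48 h, the standard error is 48 × √(2/35) = 11.47 h.

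- Critical difference at 0.0031: 2.737 × 11.47 = 31.4 h (32.4 h by t, 68 df).
- Critical difference at 0.025: 1.960 × 11.47 = 22.5 h (22.9 h by t).
- Observed 24 h: z = 24/11.47 = 2.09, one-sided p = 0.018 (0.020 by t).

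By t-test with 35 per arm, an observed 24 h passes 0.025 and fails 0.0031 when the observed SD lies between 35.5 and 50.3 h. Outside that range the two levels agree on a 24 h result. With 32 per arm the range is 33.9 to 48.0 h, so the planning SD sits at its edge.

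**4. Overall type I error if the sentence is applied.** The interim and final z-statistics are bivariate normal with correlation √0.5. Overall error is 1 − P(Z₁ < c₁, Z₂ < c₂) under no effect. Two final levels are shown: the stated 0.0219, and 0.0237, which is the nominal level that makes total spending exactly 0.025 after 0.003125 at the interim.

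| Interim rule | Final 0.0219 | Final 0.0237 |
|---|---|---|
| p < 0.0031 (baseline) | 2.32% | 2.50% |
| p < 0.025 | 3.91% | 4.05% |
| p < 0.025 and observed ≥ 24 h, SD 40 h, 35 per arm | 2.50% | 2.67% |
| same, SD 48 h, 35 per arm | 3.37% | 3.52% |
| same, SD 52 h, 35 per arm | 3.91% | 4.05% |
| same, SD 48 h, 32 per arm | 3.73% | 3.88% |

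For the 24-hour rule, c₁ is the larger of 24/SE and 1.960. At SD 52 h, 24/SE = 1.93, so the 24-hour condition no longer binds and the rule becomes a plain 2.5% test.

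A simulation with t-tests (600,000 trials, SD 48 h, 35 then 70 per arm) gave 3.91% / 4.05% for the plain rule and 3.29% / 3.44% with the 24-hour condition.

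**The case against.** The strongest reply is that the rule is already fixed. Section 6.1 gives a specific level, its source, an adjustment clause and a table that reproduces only at 0.0031. Against these stands one parenthesis that nearly repeats the power statement in Section 4.3.3. An analyst would use 0.0031, and the inflation figures describe a misapplication. On this view 'futile' is plain language for pointless to go on once superiority is shown, and no futility rule is missing because none was planned.

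Most of this stands. The harmless reading is the likelier one, and on it the error rate is unaffected. The efficacy purpose is also clear from the other sections. The reply does not show that the sentence is right. It is the one that links the interim result to the enrolment decision, and its level is not the level of the test. A stopping rule is fixed in advance so that nobody has to infer which of two levels was meant.

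It is also fair to say that the 24-hour figures depend on the per-arm number: 3.4% to 3.5% at 35, and 3.7% to 3.9% at 32. Either way they exceed 2.5%.

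**Conclusion.** The concern holds as a conflict in the stated decision rule, and it should be fixed. The designed rule is an efficacy stop at one-sided 0.0031. If the parenthesis only restates the overall level, there is no inflation. If it is applied at the interim, overall one-sided error rises from the stated 2.5% to 3.9% to 4.05% as a plain test, or to 3.4% to 3.5% with the 24-hour condition at SD 48 h and 35 per arm. With that condition the size depends on the SD, and at 40 h the excess is negligible (2.5% to 2.7%, against baselines of 2.3% to 2.5%). The figures assume an approximately normal test statistic and an interim at half the information. 'Futile' is wrong wording on either reading.

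**What to change.** Replace the sentence in Section 6.1 with: *Enrolment stops early for efficacy only if the one-sided interim p-value is below 0.0031, recomputed from the spending function at the actual information fraction.* Delete 'futile' and the parenthesis with 24 hours and 2.5%, since neither the spending function nor the table contains such a condition. If a futility look is wanted, give it its own rule.

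The cost is one reworded sentence. The spending function, sample size and power table stay as they are.

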6.3 DATA / STATISTICAL ANALYSIS

All efficacy analyses will be intent to treat. The time to bowel function recovery and hospital length of stay will be compared between the two groups using Student's t-test. Due to the short-term nature of the outcome measures we expect no censoring.

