8 TIMELINE

Upon final review of the study protocol, the signed contract shall be completed within 1-2 months. Duration of IRB/ethics approval is estimated to occur between 2-3 months after initial submission. To reach the goal of 140 patients in each study arm, at an estimated rate of 40 enrolled patients per year, the study will last at least three years. If the interim analysis indicates that 35 patients per arm is sufficient to detect a significant difference between groups, final enrollment may occur within two years after the first enrolled patient.

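### The plan adjusts the significance levels for the interim look but sets no estimate or interval for a trial that stops early for efficacy; at SD 48 h the raw difference would then average 60–66% above a true 24 h

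*Combined protocol and SAP*

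**What the plan says.** Section 4.3.3 sets the target: "The study has been designed to provide at least 80% power to detect a 24-hour decrease" at one-sided 2.5%, where "we expect a standard deviation of 48 hours" and "64 evaluable patients per group will provide the desired power". Seventy per arm are to be recruited.

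Section 6.1 places one interim analysis at 35 patients per arm. The interim level is one-sided 0.0031 and the final level 0.0219, from a third-degree power spending function. On the consequence it says: "If the design assumptions are correct, the study will stop early for efficacy with 23% probability". The table that follows gives 22.9% at the design effect and 60.0% at one and a half times that effect. Section 8 confirms that enrolment may end there: "If the interim analysis indicates that 35 patients per arm is sufficient to detect a significant difference between groups", recruitment may finish within two years.

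The same part of 6.1 also describes the interim decision differently, as a futility judgement tied to a 24-hour decrease at one-sided 2.5%.

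Section 6.3 is the whole analysis plan. Analyses are by intention to treat, no censoring is expected and, along with time to bowel recovery, "hospital length of stay will be compared between the two groups using Student"'s t-test. It mentions no point estimate, no confidence interval and no allowance for an early stop in either.

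**The concern.** An efficacy boundary selects large observed differences. The spending function protects the error rate of the test, but it does nothing to the estimate reported when the boundary is crossed. If 6.3 stays silent, the likely default is the raw mean difference with an ordinary 95% interval.

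The number of hours saved is what surgeons would take from this trial. On the plan's own assumptions, nearly one trial in four ends at the interim look, and its readers see only that selected result. A method chosen after the interim result is known would carry less weight than one fixed beforehand.

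**Working it through.** **Inputs.** From 4.3.3: difference 24 h, SD 48 h, 64 evaluable per arm, one-sided 0.025. From 6.1: interim at 35 per arm, halfway, with cubic spending. Half of 64 evaluable is 32, so both 32 and 35 per arm are shown.

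**Reproducing the plan.**
- Interim alpha: 0.025 × 0.5³ = 0.003125 (stated 0.0031), so z = 2.734.
- Group sequential size for 80% power: 63.4, so 64 per arm (stated 64).
- Chance of an early stop at 64 per arm: 23.1%. At the drift giving exactly 80% power it is 22.9%, the table's figure.

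**Difference needed to stop.** SE = 48 × √(2/n).
- 32 per arm: SE = 12.0 h; 2.734 × 12.0 = 32.8 h.
- 35 per arm: SE = 11.47 h; 2.734 × 11.47 = 31.4 h.
- With t rather than normal critical values: 34.0 h and 32.4 h.
- The threshold scales with the observed SD: 26–27 h at SD 40 and 39–41 h at SD 60.

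**Mean raw difference given a stop, true effect 24 h.** With k = 2.734 − 24/SE, the mean is 24 + SE × φ(k)/(1 − Φ(k)).
- 32 per arm: k = 0.734; 24 + 12.0 × 0.3047/0.2314 = 39.8 h (+66%).
- 35 per arm: k = 0.643; 24 + 11.47 × 0.3245/0.2602 = 38.3 h (+60%).
- A simulation of 400,000 trials using the t-test with estimated SD gave 39.9 h and 38.4 h.

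**Coverage of an unadjusted 95% interval given a stop.** (Φ(1.96) − Φ(k))/(1 − Φ(k)).
- True 24 h: (0.9750 − 0.7686)/0.2314 = 89% at 32 per arm; 90% at 35. The t-test simulation gave 88% and 90%.
- True 12 h: 40% and 45%, with mean raw differences of 37.7 h and 36.1 h.
- True 36 h: about 96%.

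**Over all trials, true 24 h.** A trial that continues averages its interim data with an equal amount of new data, so the overall bias is SE × φ(k)/2 = 12.0 × 0.3047/2 = 1.8 h. Simulated overall coverage is 94.7%.

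**What the remedies achieve.**
- Repeated interval, estimate ± 2.734 SE: half-width 31.4–32.8 h, against 22.5–23.5 h unadjusted. Coverage given a stop at 32 per arm is 1 − 0.003125/0.2314 = 98.6% at a true 24 h, and 1 − 0.003125/0.0414 = 92.5% at a true 12 h. At 35 per arm it is 98.8% and 93.2%.
- Standard mean-bias adjustment: solve θ + SE × φ(2.734 − θ/SE)/2 = observed difference. In stopped trials at a true 24 h, the average falls from 39.8 to 37.8 h (32 per arm) and from 38.3 to 36.4 h (35 per arm). That removes about 2 h of an overstatement of 14–16 h.

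**The other wording of the interim rule.** At one-sided 2.5%, the threshold would be 22.5–24.0 h, the stopping probability 52–55% by the normal calculation, and the overstatement 34–39%. That does not fit the stated 23% or the table.

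**The case against.** The strongest reply is that the plan's inference is sound. Alpha spending handles the type I error, about 77% of trials at the design effect do not stop early, and averaged over all trials the estimate is less than 2 h too high with close to nominal coverage. This stands, and it limits the point to how an early stop is reported.

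A second reply is that, for a stop at the first look, stage-wise ordering returns the unadjusted estimate and interval. Leaving them alone is therefore a recognised method with correct overall coverage, and preferring a repeated interval is a choice of criterion. That is fair. By the conditional criterion the repeated interval also falls a little short at a true 12 h (92–93%). The reason to prefer it is that readers of a stopped trial see only the selected result, and at 12 h the unadjusted interval covers only 40–45% of the time.

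Four stronger readings are tempting, and the documents do not support them:
- *The t-test causes the overstatement.* It does not; the boundary selects large estimates under any test.
- *The interval could contradict the decision to stop.* Every stopped trial has z above 2.73, so its unadjusted 95% interval excludes zero.
- *An early stop cannot report 24 h.* That depends on the observed SD. Section 6.1 itself allows for a smaller SD. If its 50% larger effect came from an SD of 32 h (48/1.5), the threshold would be 20.9–21.9 h and the mean estimate given a stop 28.3–29.1 h (+18–21%).
- *The planned interval is too narrow.* No interval is planned, and the shortfall of an unadjusted one comes mainly from its shifted centre.

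**Conclusion.** The gap is real and modest: a missing estimation rule, with no error in the test. If the SD is 48 h, the 0.0031 rule applies and the true effect is 24 h, a trial stopped at the interim would report on average 14–16 h too much, and an unadjusted 95% interval would miss the truth in about one stopped trial in ten. The overstatement is proportionally larger if the true effect is smaller, and smaller if the true effect is larger or the SD is lower. The coverage figures assume that the unreported default would be an ordinary 95% interval. The superiority conclusion does not change.

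The two descriptions of the interim rule in 6.1 have to be reconciled first, because these figures follow from 0.0031.

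**What to change.** Add to 6.3, before the interim analysis:

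- After an early efficacy stop, report the repeated confidence interval from the interim boundary (estimate ± about 2.73 SE, recalculated if the information fraction differs). Beside the raw mean difference, report a bias-adjusted estimate whose method is named in advance. State that a standard mean-bias adjustment removes only about 2 h of the overstatement given a stop, so it is not read as a full correction.
- At the final analysis, report the interval whose level matches the final boundary. If 0.0219 is kept as the nominal level, the multiplier is about 2.02. That figure is the alpha left to spend (0.025 − 0.003125); the nominal level that uses the full 0.025 is 0.0237, with multiplier about 1.98. Say which is meant.
- In 6.1, reconcile the one-sided 2.5% wording of the interim decision with the 0.0031 level.

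The cost is a few sentences and a few lines of standard code, with no change to sample size or alpha. The price is a wider interval and a less favourable estimate after an early stop.
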